In our pilot CPRD data the proportions of patients prescribed each second-line treatment varied widely; for example in 2014, the ranges across CCGs were 5-100% (SU), 0-90% (DPP4i) and 0-35% (SGLT2i). These proportions have changed over time (2014-2018) (Fig. 2), but similar patients received different first-stage treatment regimens simply according to CCG prescribing preference, or time period.

This study's design will exploit this wide variation in the choice of second-line treatment. Our CPRD pilot data suggest that 'CCG prescribing history' is a valid IV for the second-line treatment regimen prescribed. The CCG prescribing history is a strong, independent predictor of the choice of first-stage treatment intensification³¹, and balances key prognostic variables like age and baseline HbA1c. We will use this IV to estimate the relative effectiveness of alternative second-line treatments for T2DM while minimising bias from unobserved confounding. We will use an IV approach, the 2-stage residual inclusion (2SRI) which can report the appropriate estimand, the average treatment effect (ATE) for the overall population and subpopulations of interest for the three way treatment comparison (SU vs DPP4i vs SGLTis) required for objectives 2 and 4. For Objective 2, which requires a two-way comparison (SU vs DPP4i) we will use a 'Local IV estimator' which can allow for heterogeneity according to unobserved (e.g. lifestyle choices) as well as observed (e.g. baseline HbA1C) factors when reporting the relative effectiveness of the alternative second-line treatments according to individual patient risk profiles.

Overall population

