We will describe the cohort who meet the study inclusion criteria. We will include people aged 18 years or older with a T2DM diagnosis who were prescribed one of the three second-line oral antidiabetic treatments of interest between 1 January 2014 and 31 March 2020 after first-line antidiabetic treatment with metformin monotherapy. We will use a cross-sectional study design to investigate the association of the patients' ethnicity and level of deprivation in their area of residence, with the choice of second line oral antidiabetic treatment prescribed. We will use mixed-effects multivariable, multinomial logistic regression models (using a random effect to account for clustering at the CCG level) to compare the odds of initiating SGLT2i and DPP4i versus SU, and SGLT2i versus DPP4i. The covariates considered in this model will include: sex, age, time on first-line oral antidiabetic treatment (metformin monotherapy), number of patients registered at the individual's general practice, geographic region, co-prescriptions for renin-angiotensin system inhibitors (RASi) and/or statins, histories of proteinuria and hypoglycaemia, BMI (kg/m²), HbA1c (mmol/mol), smoking status, alcohol intake, and relevant comorbidities at the time of second-line antidiabetic initiation. The model will also mutually adjust for ethnicity and deprivation (using the index of multiple deprivation (IMD)). We will use this model to report any disparities in the initiation of second-line antidiabetic treatments according to ethnicity and social deprivation level.

Outputs: We will provide an assessment of whether there are inequalities in the use of second-line treatment according to ethnicity and levels of deprivation.

Objective 2: Comparative effectiveness

Design

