Effect size: between-treatment difference in mean HbA1c reduction baseline to 12 months	SU	SGLT2i	SU	SGLT2i	SU	SGLT2i
0.3	3416	1464	2615	1121	2066	886
0.4	1921	823	1471	630	1162	498
0.5	1230	527	941	403	744	319

Table 1: Required sample size (N) for the IV design according to instrument strength (level of compliance) and magnitude of effect size at 90% power and 2.5% (2-sided) level of statistical significance

Analysis

An instrumental variable (IV) analysis will address confounding by indication. The instrumental variable approach taken will be the two-stage residual inclusion (2SRI) method.²³ This approach will enable us to report comparative effectiveness across the full study populations of interest, that is, to report average treatment effects, while addressing the risk of bias from unmeasured confounding. The first stage models will estimate the probabilities for each person to be prescribed each treatment given their baseline covariates and their CCG's tendency to prescribe (TTP) that treatment. The second-stage outcome models will include generalised residuals from the first stage (propensity score) models. The outcome models will be estimated by ordinary least squares (OLS) for continuous outcomes (e.g. 1-year HbA1c), and Cox proportional hazards models for time-to-event outcomes.⁴⁵ All standard errors will be calculated with non-parametric bootstrapping, and will account for clustering of individuals within practices, and within- individual correlation introduced by repeated measures of outcomes.

Sensitivity analyses

We will undertake sensitivity analyses to consider data issues, for example by applying alternative exclusion criteria for when there is doubt about the clinical coding of T2DM⁴⁶ or the second-line treatment regimen. We will consider different assumptions about missingness patterns, for example by undertaking complete records analysis⁴⁷. We will examine the robustness of the findings to alternative statistical models including those that use traditional IV designs and risk-adjustment.

Output

We will provide estimates of the comparative effectiveness of second-line treatments with SUs vs DPP4is vs SGLT2is.

Objective 3: To examine heterogeneity in the comparative effectiveness of DPP4i versus SU

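### The Objective 1 disparity model pools 2014 to March 2020 without listing calendar time and allows for clustering by CCG only, so its odds ratios may carry a time trend and its intervals may be too narrow.

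*Protocol*

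**What the plan says.** Protocol section 4, Objective 1 (Inequalities, Design), takes people who started one of the three drug classes "between 1 January 2014 and 31 March 2020 after first-line antidiabetic treatment with metformin monotherapy". It states: "We will use a cross-sectional study design to investigate the association of the patients' ethnicity and level of deprivation". The analysis is a mixed-effects multinomial logistic model, "using a random effect to account for clustering at the CCG level". It compares SGLT2i and DPP4i with SU, and SGLT2i with DPP4i.

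The covariate list begins "The covariates considered in this model will include: sex, age, time on first-line oral antidiabetic treatment (metformin monotherapy" and goes on to "number of patients registered at the individual's general practice, geographic region", co-prescriptions, clinical history, BMI, HbA1c, smoking, alcohol and comorbidities. Ethnicity and deprivation are adjusted for each other. No year or date of initiation is listed. Time on metformin is a duration, not calendar time. The practice enters only through its list size.

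Four other places in section 4 bear on this:
- Instrumental variable design says of the prescribing shares: "These proportions have changed over time (2014-2018". The same sentence gives CCG preference or time period as the reason why similar patients received different regimens.
- The Fig. 3 caption describes pilot preference measures built by year and CCG.
- Objective 3 is restricted to 2011-2015 because SGLT2i use was low then.
- Objective 2, Analysis, says that its standard errors "will account for clustering of individuals within practices".

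**The concern.** The protocol names two non-clinical drivers of drug choice, CCG preference and calendar period. The Objective 1 model represents the first and omits the second. A CCG effect that is constant over the window cannot absorb a national trend.

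The odds ratios by ethnicity and deprivation are the whole output of Objective 1. If a group's share of initiators changes over the same years in which prescribing moved from SU towards SGLT2i, part of the trend is reported as a disparity, or part of a disparity is hidden.

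Separately, if prescribing habits differ between practices within a CCG, and ethnicity or area deprivation also clusters by practice, a model with a CCG effect alone treats correlated patients as independent and overstates its precision.

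**Working it through.** Objective 1 states no sample size, power or expected odds ratio, so there is no plan figure to reproduce. Three checks were made.

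**1. Size of the time trend, from the protocol's figures (Comparators and second-line treatment cohorts)**
- 2016 pilot shares: SGLT2i 15.4%, SU 35.4%. Odds = 15.4/35.4 = 0.44.
- 2016-2019 counts: SGLT2i 6,700, SU 6,000. Odds = 6,700/6,000 = 1.12.
- Ratio = 1.117/0.435 = 2.6, comparing one year with a four-year total that contains it. All these years lie inside the Objective 1 window. The pilot and feasibility counts may rest on slightly different bases.

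**2. Effect of leaving year out**

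For group g (0 or 1) and year t, with SU as reference:
- SGLT2i log-odds = ln(15.4/35.4) + s1 × (t − 2016) + g × ln(OR1)
- DPP4i log-odds = ln(41.4/35.4) + s2 × (t − 2016) + g × ln(OR2)

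The class probabilities are averaged over 2014 to 2019 with weight 1 per year, and 2020 with weight 0.25, each multiplied by the group's share in that year. The pooled odds ratio is then formed.

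Assumed, because the protocol does not give them: slopes (s1, s2) of (0.4, 0.15), (0.6, 0.25) and (0.8, 0.30) per year; a group share of 20%, or one moving linearly between 18% and 22%; and no other covariates. As a check on s1, these slopes imply pooled 2016-2019 SGLT2i:SU odds of 0.81, 1.08 and 1.44, which bracket the 1.12 from the counts.

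SGLT2i vs SU odds ratio with year omitted, over the three slope pairs:

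| Year-conditional OR | Constant share | Share 18% to 22% | Share 22% to 18% |
|---|---|---|---|
| 1.00 | 1.00 | 1.05-1.10 | 0.91-0.95 |
| 0.70 | 0.715-0.755 | 0.75-0.83 | 0.68-0.69 |
| 0.50 | 0.52-0.58 | 0.55-0.63 | 0.49-0.53 |

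Shrinkage on the log scale with constant share, for OR 0.70:
- 1 − ln(0.715)/ln(0.70) = 1 − 0.335/0.357 = 6%
- 1 − ln(0.755)/ln(0.70) = 1 − 0.281/0.357 = 21%

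The 0.50 row gives the same range.

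**3. Effect of ignoring practice**

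Design effect = 1 + (m − 1) × ICC × ρ, where m is patients per practice, ICC is the residual practice-level correlation in drug choice, and ρ is the within-practice correlation of the exposure. The standard error is understated by the square root. The protocol gives none of the three, so all values are assumed.

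| m | ICC | ρ | Design effect | SE factor | Coverage of a nominal 95% interval |
|---|---|---|---|---|---|
| 10 | 0.01 | 0.1 | 1.01 | 1.00 | 95% |
| 20 | 0.05 | 0.3 | 1 + 19 × 0.05 × 0.3 = 1.29 | 1.13 | 92% |
| 20 | 0.05 | 1 | 1 + 19 × 0.05 = 1.95 | 1.40 | 84% |
| 40 | 0.05 | 1 | 1 + 39 × 0.05 = 2.95 | 1.72 | 75% |

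A simulation of a CCG-adjusted logistic model that ignores practice (true log OR 0, 20 patients per practice, 150 runs, CCG as fixed effects) points the same way. For residual practice SDs of 0, 0.3, 0.5 and 0.8, the ratio of empirical to model standard error was 0.99, 1.00, 1.18 and 1.33, and coverage was 95%, 97%, 90% and 83%.

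**The case against.** **Averaging over year is not bias.** With a constant mix, the model without year gives a period-averaged odds ratio. That is a defensible target for a study described as cross-sectional, and a null stays null. This stands: the 6-21% is a change of estimand, not an error.

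**Confounding needs a drift that nobody has shown.** The protocol gives no ethnic or deprivation mix by year. This also stands. A reader might infer that disparities will be understated, but the table shows that a falling share moves 0.70 to 0.68-0.69, away from 1. Neither the presence nor the direction of bias follows from the document.

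**The trend can be made to look larger than it is within the window.** Subtracting the 2016-2019 counts from the 2011-2019 counts leaves 1,300 SGLT2i and 32,000 SU for 2011-2015, and a late-to-early odds ratio of 1.117/0.0406 = 27.5. That block includes 2011-2013, before the window opens, so 27.5 should not be used as the size of the shift.

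**Objective 2 does not say that drug choice clusters by practice.** It allows for practice clustering in the standard errors of outcome effects. The protocol also explains why it works at CCG level: several parties besides the GP may shape the choice. List size and region are adjusted for as well. A reader might infer that the Objective 1 intervals are certainly too narrow, but without an ICC or cluster size the understatement could be nil. What remains is that practice clustering was thought worth allowing for in the same data, and list size as a covariate does not do that.

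**The list may be open and detail may sit in an analysis plan.** The wording on covariates is not clearly exhaustive. But the protocol fixes the model, the level of the random effect and covariates as minor as alcohol intake. Leaving out a driver that it names itself is a choice in the stated model, not detail deferred.

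**Conclusion.** The point holds in conditional form. As written, the Objective 1 model leaves out calendar time, a predictor that the protocol itself identifies and whose strength shows in its own figures (SGLT2i:SU odds of 0.44 in 2016, 1.12 over 2016-2019).

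- The odds ratios may be confounded in either direction if mix drifts with time. A four-point drift in a group's share would move a true 1.0 to about 1.05-1.10 or 0.91-0.95, on assumed slopes of 0.4-0.8 per year. Shifts of that size matter where modest disparities are the finding of interest.
- With constant mix, the only consequence is a period-averaged odds ratio, about 6-21% nearer the null on the log scale.
- Intervals may be too narrow, by a standard-error factor of 1.0 to about 1.7, only if practice variation remains after the listed adjustments and ethnicity or deprivation clusters by practice.

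The omission of calendar time is the stronger half and the practice level the weaker. The change is worth making because it is nearly free, not because bias has been shown.

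**What to change.** In Objective 1, Design, add calendar year of initiation to the multinomial model, as year indicators or a spline. Report year-by-ethnicity and year-by-IMD terms as a secondary check on whether a single pooled odds ratio describes the whole window. If a period-averaged odds ratio is the intended target, say so and give the year-adjusted one beside it.

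Account for practice clustering, by a practice random effect within CCG or by practice-clustered standard errors, as Objective 2 already does for its own standard errors.

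No new data are needed: the date of first second-line prescription already defines baseline, and practice is already used for list size. The cost is slightly longer fitting and possibly wider intervals.

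### Objective 1's only reporting model conditions on region, CCG and the other exposure, so it gives near within-area odds ratios, while the stated output is inequality in use without qualification

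*Protocol*

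**What the plan says.** Protocol section 4, Objective 1 (Design) plans "mixed-effects multivariable, multinomial logistic regression models (using a random effect to account for clustering at the CCG level"), comparing SGLT2i and DPP4i with SU, and SGLT2i with DPP4i. Besides clinical factors, the covariates include practice list size and "geographic region, co-prescriptions for renin-angiotensin system inhibitors (RASi) and/or statins". The two exposures enter together: "The model will also mutually adjust for ethnicity and deprivation (using the index of multiple deprivation (IMD").

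The protocol then names the source of the result: "We will use this model to report any disparities in the initiation of second-line antidiabetic treatments according to ethnicity and social deprivation level". The stated output is: "We will provide an assessment of whether there are inequalities in the use of second-line treatment according to ethnicity and levels of deprivation". Neither sentence is limited to differences within an area or at a given level of deprivation. No crude, demographic-only or staged model is named.

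On the role of place, the section on the instrumental variable design reports for the pilot data that "in 2014, the ranges across CCGs were 5-100% (SU), 0-90% (DPP4i) and 0-35% (SGLT2i"). It adds that "similar patients received different first-stage treatment regimens simply according to CCG prescribing preference", and the same sentence also names time period.

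**The concern.** The random effect is introduced only to handle clustering. In a logistic model with sizeable clusters it also changes what is estimated: the odds ratio moves close to a within-CCG comparison. If an ethnic or deprived group lives disproportionately in CCGs with low uptake of a drug, its members receive that drug less often, yet this part of the gap is largely absorbed by the CCG and region terms.

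Mutual adjustment raises a separate issue, mainly for ethnicity. Area deprivation can lie on the path from ethnicity to treatment, so holding IMD fixed removes that part of an ethnic gap.

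Objective 1 exists to say whether inequalities exist. A conditional odds ratio near 1 could be read as showing none when overall use differs.

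**Working it through.** The protocol gives no sample size, power or odds ratio for Objective 1, so there is no figure to reproduce. The check asks how far the planned structure and an overall comparison can diverge. All numerical settings below are assumptions unless a source is given.

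**1. Two-area arithmetic.** Overall share = w × low + (1 − w) × high, where w is the fraction of a group living in low-uptake areas. There is no difference within areas, so the within-area odds ratio is 1.00.

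- Central case: uptake 10% and 30%; w = 0.65 (minority) and 0.45 (majority).
  - Minority: 0.65 × 10% + 0.35 × 30% = 17%.
  - Majority: 0.45 × 10% + 0.55 × 30% = 21%.
  - Odds ratio: (0.17/0.83) / (0.21/0.79) = 0.77.
- Wide case: uptake 5% and 35%; w = 0.75 and 0.40.
  - Shares: 3.75% + 8.75% = 12.5%, and 2% + 21% = 23%. Odds ratio 0.48.
- Narrow case: uptake 15% and 25%; w = 0.60 and 0.50.
  - Shares: 9% + 10% = 19%, and 7.5% + 12.5% = 20%. Odds ratio 0.94.

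**2. Simulation of the planned structure.** The model was simplified to SGLT2i versus not, with a CCG random intercept, both exposures, and nine regions in or out; clinical covariates were omitted. Total N was 25,700 (the Objective 2 sample size) or 75,000 (38,000 + 29,000 + 8,000, the long-term outcomes cohort). With 100 or 200 CCGs this gives about 128 to 750 patients per CCG. The CCG log-odds SD was 0.5 or 0.8, and minority share was set to fall as uptake rises. Each setting was run on one simulated data set, so the second decimals carry sampling error.

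| Setting | Estimate | Crude OR | Planned-structure OR |
|---|---|---|---|
| Area route only, no within-area effect (12 settings) | Ethnicity | 0.49–0.81 | 0.94–1.01 |
| Same | Deprivation | 0.67–0.90 | 0.95–1.03 |
| Area route plus deprivation effect (log-OR −0.4), no direct ethnicity effect | Ethnicity | 0.65 | 1.01–1.02 |
| Same | Deprivation | 0.57 | 0.66 |
| Deprivation effect only, no area effect | Ethnicity | 0.86 | 0.94 |
| Within-area ethnicity log-OR −0.3, group living in high-uptake areas | Ethnicity | 1.11 | 0.75 |

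The random intercept does almost all of this: adding region moved the odds ratios by at most 0.01. Partial pooling can leave a small between-area remnant.

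**3. Reading the table.** The first rows show a between-area gap disappearing from the planned estimate. The last row shows the reverse: the overall comparison hides a within-area disparity that the planned model finds. The two quantities answer different questions, and neither can stand in for the other.

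**The case against.** The strongest reply is that the planned model answers a proper question: whether comparable patients in the same area receive different drugs. The protocol frames Objective 1 as an association with choice of treatment and nowhere promises a total-access measure. This stands, and it is a reason to keep the model. It does not remove the mismatch with an output worded as inequality in use.

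Second, a statistical analysis plan may add crude or staged estimates, and the protocol plans to describe the cohort. That is possible, but the protocol itself fixes which model disparities are reported from.

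Third, section 4, The key assumptions, states that CCG prescribing history balanced the observed covariates. If ethnicity and IMD were among them, the area route would be small. Both are listed as patient-level covariates, but the Fig. 3 caption speaks of clinical risk factors, the figure is not shown, and the text does not settle the matter. The mutual-adjustment issue would remain either way.

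Fourth, the 2014 ranges are weak evidence of how far CCGs truly differ. They come from 4,450 patients; with an assumed 200 CCGs that is about 22 each. In a check using one common SGLT2i rate (assumed 5–15%), chance alone gave a median highest CCG of 23–36% and a lowest of 0%. So that range does not establish that 10% versus 30% areas are realistic. The protocol's statements that CCG history strongly predicts treatment still support real variation.

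A reader might infer three stronger claims, none of which the documents support:

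- *Objective 1 will report odds ratios near 1.* That needs the whole gap to lie between areas or to act through deprivation, which nothing in the protocol shows.
- *Mutual adjustment spoils the deprivation result.* Ethnicity is plausibly a confounder there, so adjusting is sound; deprivation gaps within a CCG stay visible (0.57 crude, 0.66 adjusted above).
- *The overall estimate should replace the planned one.* The reversal case (1.11 against 0.75) shows that this could hide a real disparity.

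**Conclusion.** The point holds as a mismatch between estimand and conclusion, not as an error in the model. The single named model yields odds ratios that are close to within-area and, for ethnicity, at equal deprivation; the output is worded without either limit. A gap between areas, or an ethnic gap acting through deprivation, could therefore be understated.

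Under the assumptions shown, an overall odds ratio of 0.77 (range 0.48 to 0.94) corresponds to 1.00 within area. These figures rest on assumed area splits, uptake levels and CCG sizes. The true size and direction cannot be obtained from the protocol, and the reported covariate balance may mean that the area route is small. The case for change is that it is cheap and alters what Objective 1 may legitimately conclude.

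**What to change.** Keep the planned model and pre-specify beside it:

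- **Model A, for each exposure:** age, sex and clinical need, without region, practice size or the CCG effect, and with standard errors clustered by CCG. Leave IMD out of the ethnicity model; keep ethnicity in the deprivation model as a confounder.
- **Model B, for ethnicity:** model A plus IMD.

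The deprivation version of A and the ethnicity version of B contain the same terms, so this amounts to two extra fits.

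Report A, B and the planned model in one table. Label A as the need-adjusted overall disparity and the planned odds ratios as conditional, within-area disparities. State in advance that absence of inequality will not be concluded from the conditional model alone.

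The cost is two fits on data already held, one table, and two estimands to explain to readers. Odds ratios also shift when terms are added even without confounding, so the change from A to the planned model should not be read as an exact share explained by place.

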Secondary outcomes will include: change in HbA1c at 2-years, and change in BMI, SBP, and eGFR all at 1and 2-years. We also reported the time to the following first events before 2-years follow-up: (a) a 40% decline in eGFR from baseline, which could be a marker for the rarer end-stage kidney disease (ESKD) outcome,²² (b) a major adverse kidney event (MAKE), a composite outcome for the earliest of a decline in eGFR from baseline of 40%, ESKD, and all-cause mortality,(c) heart failure hospitalisation, (d) 3-point major adverse cardiovascular event (MACE), a composite outcome for the earliest of myocardial infarction, stroke, and CVD death, and (e) all-cause mortality. We also reported time to myocardial infarction and stroke individually.

Sample size calculation

The study will include approximately 25,700 (SU=6000, DPPi4=13,000, SGLT2i=6,700) patients who meet the eligibility criteria. The FDA recommends that an average between-treatment difference in the HbA1c change from baseline of 0.4% (e.g. from 8.0% to 7.6%) is of clinical significance⁴². The assumed standard deviation of 2.4 is taken from a previous study of patients with T2DM recruited from CPRD⁴³. We follow methodological recommendations for sample size calculations with IV designs, by assuming a 'base case' level of non-compliance of 10%, but also consider scenarios with alternative levels¹. We require 90% power at the 5% (2-sided) level of statistical significance. We follow methodological recommendations for sample size calculations with IV designs, it will not perfectly predict the treatment received, and so we assume the 'base case' compliance (the proportion of patients in who actually receive the treatment predicted by the IV) is 80%, but also consider scenarios where the V is weaker (70% compliance) and stronger (90%). Table 1 shows the requisite sample sizes for the two treatment groups projected to have fewest patients (SU and SGLT2i). The anticipated sample sizes will be more than sufficient across these scenarios for detecting whether the overall estimates of treatment effectiveness are statistically significant.

With the projected sample sizes, we can also report estimates of treatment effectiveness with sufficient precision for major subgroups of prime interest, for example according to established CVD (or not), and broad categories by age, and levels of baseline HbA1c, and eGFR.

	Level of	compliance (IV strengt	th)		
70%			80)%	909	%

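### Table 1 scales the IV effect by the compliance level, the most favourable reading of the protocol's own definition, and its cells match 80% power instead of the stated 90%

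*Protocol*

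**What the plan says.** In the protocol, section 4, Objective 2, Sample size calculation:

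- The clinically relevant effect is a "difference in the HbA1c change from baseline of 0.4" per cent, and Table 1 also covers 0.3 and 0.5. On spread: "The assumed standard deviation of 2.4 is taken from a previous study".
- The text states: "We require 90% power at the 5% (2-sided) level of statistical significance". The Table 1 caption reads "at 90% power and 2.5% (2-sided) level of statistical significance".
- Instrument strength has two base cases in one paragraph. The first is a "level of non-compliance of 10%, but also consider scenarios with alternative levels". The second is compliance, "the proportion of patients in who actually receive the treatment predicted by the IV) is 80" per cent, with 70% as the weaker and 90% as the stronger scenario.
- Table 1 covers SU and SGLT2i, the two smallest groups, projected at 6,000 and 6,700.
- The conclusion is: "The anticipated sample sizes will be more than sufficient across these scenarios". The next paragraph extends the claim to adequate precision in major subgroups (established CVD, age, baseline HbA1c, eGFR).

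The Instrumental variable design section gives one pilot illustration of the spread in prescribing. In 2014 "the ranges across CCGs were 5-100% (SU), 0-90% (DPP4i) and 0-35% (SGLT2i").

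**The concern.** Multiplying the effect by c is right if patients who miss the predicted drug add nothing to the contrast between the two drugs. Here every eligible patient starts one of three active classes. In a comparison of SU with SGLT2i, a patient who misses the predicted drug and gets the other one cancels a patient who complied. The 1/c² scaling therefore understates the required numbers unless all such patients go to DPP4i.

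Instrument strength drives power in an IV study, and Table 1 is the only power statement in the protocol. If it is too favourable, a null SU versus SGLT2i result could be read as evidence of no difference when the design could not have shown one. The risk is greatest in a subgroup. The two base cases, two significance levels and unmatched power also leave the reader unable to tell which calculation was done.

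**Working it through.** **Inputs.** SD 2.4; differences 0.3, 0.4, 0.5; c = 70%, 80%, 90%; projected 6,000 SU and 6,700 SGLT2i (all from the sample size section). Every row of Table 1 has SU:SGLT2i close to 70:30 (for example 1,471:630), so the fraction f = 0.7 is inferred from the table.

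**1. Reproducing Table 1.** For two means, N = [SD × (z_alpha + z_power) / (k × difference)]² / [f(1 − f)], where k is the treatment contrast. For 0.4 at 80%, with k = c:

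- 80% power, 5% two-sided: [2.4 × (1.960 + 0.842) / 0.32]² / 0.21 = 2,102, split 1,472 / 631. Printed: 1,471 / 630.
- 90% power, 5% two-sided: [2.4 × (1.960 + 1.282) / 0.32]² / 0.21 = 2,814, split 1,970 / 844.
- 90% power, 2.5% two-sided: 2,327 / 997.

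All nine cells match the first line to within two patients. None matches at 90% power and either two-sided level. The table thus uses k = c and 80% power.

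**2. The contrast implied by the definition.** Let a share c receive the drug predicted by the IV.

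- If all others receive the comparator: k = c − (1 − c) = 2c − 1, i.e. 0.4, 0.6, 0.8.
- If all others, in both groups, receive DPP4i: k = c, i.e. 0.7, 0.8, 0.9.

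Moving from c to 2c − 1 multiplies N by [c/(2c − 1)]²: (0.7/0.4)² = 3.06; (0.8/0.6)² = 1.78; (0.9/0.8)² = 1.27.

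**3. Power at the projected sizes with k = 2c − 1.** SE = 2.4 × √(1/6,000 + 1/6,700) = 0.0427. Power = Φ(k × difference / SE − z_alpha). For 0.3 at 70%: 0.12/0.0427 = 2.81, and Φ(2.81 − 1.96) = 80.3%; at 2.5% two-sided, Φ(2.81 − 2.24) = 71.6%.

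| Difference | c = 70% | c = 80% | c = 90% |
|---|---|---|---|
| 0.3 | 80.3% (71.6%) | 98.8% (97.6%) | >99.9% |
| 0.4 | 96.3% (93.4%) | >99.9% | >99.9% |
| 0.5 | 99.7% (99.3%) | >99.9% | >99.9% |

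Figures are at 5% two-sided, with 2.5% in brackets. For 0.3 at 70%, 90% power at 5% and the projected 6,000:6,700 split would need 7,967 SU and 8,897 SGLT2i patients. With k = c the same cell has 99.8% power.

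**4. Subgroups.** The protocol gives no subgroup sizes, so half and a quarter of each group are assumptions. A quarter doubles the SE to 0.0853. Power for 0.4 at 5% two-sided:

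| Subgroup | c | k = 2c − 1 | k = c |
|---|---|---|---|
| Half | 70% | 76% | 99.6% |
| Quarter | 70% | 47% | 91% |
| Quarter | 80% | 80% | 96% |

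None of these figures allows for clustering or missing outcomes.

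**5. Base case.** Non-compliance of 10% is compliance of 90%, which the same paragraph labels the stronger scenario.

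**The case against.** The strongest reply is that 2c − 1 is a worst case. There are three drugs, and DPP4i is the largest group (13,000 of 25,700). If patients who miss the predicted SU split between the other two classes in proportion to group size (an assumption), the contrast at 70% is 0.7 − 0.3 × 6,700/19,700 = 0.60. Power for 0.3 is then about 98.8%, and all nine cells are comfortable. This stands as a limit on the point: the documents fix a range for the contrast, not a value. It does not rescue the table, which takes the top of that range without saying so.

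It is also fair to say that this is a fixed database cohort, so no recruitment depends on Table 1. The protocol also describes the pilot instrument as strong and commits to re-checking the IV assumptions in the full data. It gives no first-stage figure, however, so 70–90% compliance for SGLT2i cannot be checked.

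A reader might go further and treat the 0–35% SGLT2i range as capping the contrast at 0.35. The documents do not support that. The range is a 2014 example, the effectiveness cohort is 2016–2019, shares are said to have changed over 2014–2018, and SGLT2i is projected at 6,700/25,700 = 26% overall. SU, the other arm, ranged over 5–100%. Even at 0.35, power for 0.4 is 90.7% at 5% two-sided (69% for 0.3). Nor can a first-stage R-squared be derived from that range without assuming a between-CCG SD that the protocol does not give.

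**Conclusion.** The point holds in a limited form. Table 1 uses the most favourable contrast compatible with the protocol's definition of compliance. At the conservative end, the blanket adequacy statement is unsupported for one cell (0.3 at 70%: 80% power at 5%, 72% at 2.5%, against the stated 90%). A reader might infer that the study is underpowered overall, but that does not follow: eight of nine cells keep at least 90% power, and 0.4 at 80% stays above 99.9%. At Table 1's own 70:30 split, three cells at 2c − 1 would need more than 6,000 SU patients (14,010, 7,881 and 6,227 at 90% power, 5%), but the projected split is about 47:53.

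The subgroup claim is weaker, falling to about 47% power for 0.4 in a quarter-size subgroup at 70% compliance. The 2014 SGLT2i range does not demonstrate 70–90% compliance, though it does not exclude it for later years.

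The inconsistencies do not depend on the choice of contrast: two base cases, two significance levels, and cells that match 80% power. The calculations assume SD 2.4, a normal approximation, and no clustering or missing outcomes.

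**What to change.** Recompute Table 1 at the stated 90% power with one significance level, one base case and the projected 6,000:6,700 allocation in place of 70:30. State the contrast explicitly: either use 2c − 1 as the conservative bound, with c as the upper bound and the reason for any value between, or replace the compliance rate with the first-stage strength for each drug pair from the latest pilot years. Then replace the overall and subgroup adequacy sentences with the resulting power or detectable differences, giving the assumed subgroup sizes.

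As a guide, at 90% power, 5% two-sided and k = 2c − 1, the detectable difference overall is 3.24 × 0.0427 / k. This is about 0.35, 0.23 and 0.17 at 70%, 80% and 90% compliance, and double that in a quarter-size subgroup.

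The cost is a recalculation and a few sentences, plus a first-stage summary from pilot data already held if that route is taken. No patients are added. The stated figures become somewhat less favourable.
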